9.4.3 Safety

Safety evaluation will include assessments of adverse experiences, medical history, physical examinations, vital signs, and laboratory assessments at baseline and throughout the study period. Local laboratories may be used for this study.

10.0 REGULATORY AND REPORTING REQUIREMENTS

The entities providing oversight of safety and compliance with the protocol require reporting as outlined below.

The Washington University Human Research Protection Office (HRPO) requires that all events meeting the definition of unanticipated problem or serious noncompliance be reported as outlined in Section 10.2.

The FDA requires that all serious and unexpected adverse events be reported as outlined in Section 10.6. In addition, any fatal or life-threatening adverse experiences where there is a reasonable possibility of relationship to study intervention must be reported.

10.1 Definitions

10.1.1 Adverse Events (AEs)

Definition: any unfavorable medical occurrence in a human subject including any abnormal sign, symptom, or disease.

Grading: the descriptions and grading scales found in the revised NCI Common Terminology Criteria for Adverse Events (CTCAE) version 4.0 will be utilized for all toxicity reporting. A copy of the CTCAE version 4.0 can be downloaded from the CTEP web site: <http://ctep.cancer.gov/reporting/ctc.html>. Grade 1-2 events will be recorded for the first fifty enrolled patients. Subsequently, only events graded as 3 or greater will be recorded. Fifty patients should be sufficient to estimate the true incidence of any adverse event to within $\pm 14\%$ with 95% confidence intervals.

Attribution (relatedness), Expectedness, and Seriousness: the definitions for the terms listed that should be used are those provided by the Department of Health and Human Services' Office for Human Research Protections (OHRP). A copy of this guidance can be found on OHRP's website: (<http://www.hhs.gov/ohrp/policy/AdvEvntGuid.htm>).

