14.0 STATISTICAL ANALYSIS METHODS AND SAMPLE SIZE

14.1 Analysis Populations

Intent-to-Treat - The intent-to-treat (ITT) population will be defined as all patients who receive at least one dose of decitabine.

Efficacy-Evaluable - The efficacy-evaluable (EE) population will be defined as all patients who receive at least one cycle of treatment.

Safety - The safety population will be defined as all patients with at least one dose of decitabine.

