14.2.4 Safety Analysis

Extent of Exposure – Duration (number of cycles/infusions) of decitabine doses (cumulative and intensity) will be summarized.

Adverse Events - All adverse events will be coded using NCI CTCAE v. 4.0. The incidence of treatment-emergent adverse events (number and percent of patients reporting the adverse event at least once during the study) will be summarized. In addition, adverse events will be summarized by investigator attribution of relationship to study medication and by grade. Similar summaries will be provided by treatment cycle.

Clinical Laboratory Evaluation – Applicable laboratory parameters will be graded according to NCI CTCAE version 4.0. The incidence of maximum grade (number and percent of patients experiencing the maximum grade during the study) will be summarized for each laboratory parameter. Similar summaries will be provided by treatment cycle. Graphical displays of select hematological parameters will also be provided.

Vital Signs, Physical Findings, and Other Safety Observations – Vital signs, findings from physical examinations, ECOG scores and weights will be presented in listing format.

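### Grade 1-2 adverse events are recorded only for the first 50 enrolled, but the safety section sets no matching denominator; over 125 dosed patients, incidences of events no worse than grade 2 would be understated by 60% and any-grade incidences by 0 to 60%.

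*Combined protocol and SAP*

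**What the plan says.** Section 10.1.1 sets the recording rule: "Grade 1-2 events will be recorded for the first fifty enrolled patients. Subsequently, only events graded as 3 or greater will be recorded". It justifies the cut-off by precision: "Fifty patients should be sufficient to estimate the true incidence of any adverse event to within" ±14% with 95% confidence. All five protocol copies in the file carry this rule (it is numbered 10.1 in two of them).

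Section 14.1 defines one safety set: "The safety population will be defined as all patients with at least one dose of decitabine". Section 14.3 plans 25 patients and then 100 more, and Section 14.2.2 speaks of 125 enrolled.

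Section 14.2.4 plans the tables: "The incidence of treatment-emergent adverse events (number and percent of patients reporting the adverse event at least once during the study) will be summarized". It adds that "adverse events will be summarized by investigator attribution of relationship to study medication and by grade", with similar summaries by cycle. It does not refer to the cut-off in 10.1.1 and names no denominator for any of these percentages.

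**The concern.** The recording rule and the analysis section do not fit together. From the 51st enrolled patient on, a grade 1-2 event is missing by design, which is different from not having occurred. A programmer who takes the only safety population defined, and applies "number and percent of patients reporting the adverse event at least once during the study" to it, will count those later patients as free of grade 1-2 toxicity.

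The percentages for grade 1-2 and for any grade would then be too low, and the tables by grade, attribution and cycle would mix two recording regimes without saying so. A reader of the report could not see this from the table and might take the non-laboratory low-grade profile to be milder than it was.

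**Working it through.** **Inputs from the documents.** Grade 1-2 events are recorded in the first 50 enrolled (10.1.1). Planned enrolment is 25 + 100 = 125 (14.3). The claimed precision is ±14 points at 95% confidence with 50 patients (10.1.1).

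**Assumptions, because the documents are silent.** The number dosed, N, is taken as 125, with 110 and 100 as sensitivity values. The share s of patients with a given event whose worst grade is 3 or higher is varied from 0 to 1. True rates are taken as equal in early and later patients, and all of the first 50 enrolled are taken as dosed.

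**Step 1: the plan's own figure.** The worst-case half-width at an incidence of 50% is 1.96 x sqrt(0.25/50) = 0.1386, or 13.9 points. The stated ±14% reproduces, and it does so with 50 as the denominator.

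**Step 2: how many patients lack low-grade recording.** 125 - 50 = 75, and 75/125 = 60%.

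**Step 3: events whose worst grade is 1-2, tabulated over all dosed.** Reported/true = 50/125 = 0.40, an understatement of 60%. A true 20% appears as 8%, 40% as 16%, and 60% as 24%. The absolute shortfall is 0.60 times the true incidence of worst-grade 1-2 events, so it passes 14 points once that incidence exceeds 0.14/0.60 = 23%.

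**Step 4: any-grade incidences.** Patients who reach grade 3 or higher are captured throughout. With f = 50/N, reported/true = f + (1 - f) x s, so the relative understatement is (1 - f) x (1 - s). At N = 125 this is 0.60 x (1 - s).

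| s | N = 125 | N = 110 | N = 100 |
|---|---|---|---|
| 0 | 60% | 54.5% | 50% |
| 0.10 | 54% | 49.1% | 45% |
| 1/6 | 50% | 45.5% | 41.7% |
| 0.25 | 45% | 40.9% | 37.5% |
| 0.50 | 30% | 27.3% | 25% |
| 0.75 | 15% | 13.6% | 12.5% |
| 1 | 0% | 0% | 0% |

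Examples at N = 125 with a true any-grade incidence of 60%:
- 5 points at grade 3 or higher: 0.4 x 60 + 0.6 x 5 = 27% reported.
- 10 points at grade 3 or higher: 0.4 x 60 + 0.6 x 10 = 30% reported, exactly half.
- 30 points at grade 3 or higher: 0.4 x 60 + 0.6 x 30 = 42% reported.

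**Step 5: when the loss exceeds half.** This requires s < 1 - 0.5/(1 - f). The threshold is 1/6 at N = 125 and 1/12 at N = 110. At N = 100 it is 0, so a loss of more than half cannot occur.

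**The case against.** The strongest reply is that no biased table has actually been specified. Section 14.2.4 names no denominator, and the one sentence that links low-grade recording to a sample size, in 10.1.1, justifies stopping at 50 because 50 patients give adequate precision. That makes sense only if those rates are to be estimated from the 50. This stands as evidence of intent, and it means the all-dosed denominator must be called an inference. It does not remove the problem: the intent was carried into neither 14.1 nor 14.2.4, and the only safety set defined there is everyone dosed.

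A reader might also infer that every any-grade incidence will be understated by more than half. The documents do not support that. Grade 3 or higher events are recorded in all patients, so the any-grade loss depends on s, which is not given, and exceeds half only below the thresholds in Step 5. It depends on the number dosed as well, which is also not given. The drop-out allowance of up to 20% in 14.2.2 concerns usability in the molecular analysis and does not settle that number.

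Nor does the whole safety profile become unreliable. Grade 3 or higher incidences and the reporting of serious events do not depend on the cut-off. The laboratory maximum-grade tables in 14.2.4 are graded from laboratory parameters, so they need not be affected. This part of the objection stands in full.

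**Conclusion.** The point holds as a mismatch between the recording rule and the planned tables. It goes beyond missing detail, because following 14.1 and 14.2.4 literally gives percentages that are too low. With all dosed patients as denominator, 125 dosed and equal true rates early and late, incidences of events whose worst grade is 1-2 are understated by 60%, and any-grade incidences by 0 to 60% according to s. The maximum falls to 54.5% at 110 dosed and 50% at 100 dosed. The ±14% in 10.1.1 does not describe a table computed over all dosed patients. The effect is confined to adverse event tables that include grade 1-2 events.

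**What to change.** Add to Section 14.2.4:

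- Grade 1-2 and any-grade incidences, including those by attribution and by cycle, are computed in the treated patients among the first 50 enrolled, with the actual number of such patients as denominator.
- Grade 3 or higher incidences are computed in the full safety population.
- Each table, and each block of rows in a by-grade table that combines the two sets, is labelled with its denominator.

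The denominator should not be fixed at 50. The cut-off counts enrolled patients while the safety population counts dosed ones. If one of the first 50 is never dosed, a fixed 50 would either include an undosed patient or bring in a later patient whose low-grade events were not recorded.

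With this change the understatement disappears, and the worst-case half-width is the plan's own 13.9 points, slightly wider if fewer than 50 were treated. The low-grade rates then describe early enrollees, the first 25 of whom come from the lead centre under 14.3, and a footnote should say so. The cost is a short addition to the text and one further table, with no new data and no change to any clinical rule.

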10.1.2 Serious Adverse Event (SAE)

Definition: any adverse drug experience occurring at any dose that results in any of the following outcomes:

- Death
- A life-threatening adverse drug experience
- Inpatient hospitalization or prolongation of existing hospitalization
- A persistent or significant disability/incapacity (i.e., a substantial disruption of a person's ability to conduct normal life functions)
- A congenital anomaly/birth defect

- Any other experience which, based upon appropriate medical judgment, may jeopardize the subject and may require medical or surgical intervention to prevent one of the outcomes listed above

All unexpected SAEs must be reported to the FDA.

10.1.3 Unexpected Adverse Experience

Definition: any adverse drug experience, the specificity or severity of which is not consistent with the current investigator brochure (or risk information, if an IB is not required or available).

Events that are both serious AND unexpected must be reported to the FDA.

10.1.4 Life-Threatening Adverse Experience

Definition: any adverse drug experience that places the subject (in the view of the investigator) at immediate risk of death from the reaction as it occurred, i.e., it does not include a reaction that, had it occurred in a more severe form, might have caused death.

Life-threatening adverse experiences must be reported to the FDA.

10.1.5 Unanticipated Problems

Definition:

- unexpected (in terms of nature, severity, or frequency) given (a) the research procedures that are described in the protocol-related documents, such as the IRB-approved research protocol and informed consent document; and (b) the characteristics of the subject population being studied;
- related or possibly related to participation in the research (in this guidance document, possibly related means there is a reasonable possibility that the incident, experience, or outcome may have been caused by the procedures involved in the research); and
- suggests that the research places subjects or others at a greater risk of harm (including physical, psychological, economic, or social harm) than was previously known or recognized.

10.1.6 Noncompliance

Definition: failure to follow any applicable regulation or institutional policies that govern human subjects research or failure to follow the determinations of the IRB. Noncompliance may occur due to lack of knowledge or due to deliberate choice to ignore regulations, institutional policies, or determinations of the IRB.

10.1.7 Serious Noncompliance

Definition: noncompliance that materially increases risks, that results in substantial harm to subjects or others, or that materially compromises the rights or welfare of participants.

10.1.8 Protocol Exceptions

Definition: A planned deviation from the approved protocol that are under the research team's control. Exceptions apply only to a single participant or a singular situation.

Local IRB Pre-approval of all protocol exceptions must be obtained prior to the event. For secondary sites, the Washington University PI will issue approval of the exception, but it must also be submitted to the local IRB with documentation of approval forwarded to Washington University. Washington University IRB approval is not required for protocol exceptions occurring at secondary sites.

10.2 Reporting to the Human Research Protection Office (HRPO) at Washington University:

The PI is required to promptly notify the IRB of the following events:

- Any unanticipated problems involving risks to participants or others which occur at WU, any BJH or SLCH institution, or that impacts participants or the conduct of the study.
- Noncompliance with federal regulations or the requirements or determinations of the IRB.
- Receipt of new information that may impact the willingness of participants to participate or continue participation in the research study.

These events must be reported to the IRB within **10 working days** of the occurrence of the event or notification to the PI of the event. The death of a research participant that qualifies as a reportable event should be reported within **1 working day** of the occurrence of the event or notification to the PI of the event.

10.3 Reporting to the Quality Assurance and Safety Monitoring Committee (QASMC) at Washington University

The PI is required to notify the QASMC of any unanticipated problem occurring at WU or any BJH or SLCH institution that has been reported to and acknowledged by HRPO as reportable. (Unanticipated problems reported to HRPO and withdrawn during the review process need not be reported to QASMC.)

QASMC must be notified within **10 days** of receipt of IRB acknowledgment via email to a QASMC auditor.

10.4 Reporting Requirements for Secondary Sites

The research team at each secondary site is required to promptly notify the Washington University PI and research coordinator of all reportable events (as described in Section 7.6) within **1 working day** of the occurrence of the event or notification of the secondary site's PI of the event. This notification may take place via email if there is not yet enough information for a formal written report (using either an FDA MedWatch form if required or an institutional SAE reporting form if not). A formal written report must be sent to the Washington University PI and research coordinator within **10 working days** of the occurrence of the event or notification of the secondary site's PI of the event. The death of a research participant that qualifies as a reportable event should be reported within **1 working day** of the occurrence of the event or notification of the secondary site's PI of the event.

The research team at a secondary site is responsible for following its site's guidelines for reporting applicable events to its site's IRB according to its own institutional guidelines. The research team at Washington University is responsible for reporting all applicable events to the FDA.

10.5 Reporting to Secondary Sites

The Washington University PI (or designee) will notify the research team at each secondary site of all reportable events that have occurred at other sites within **10 working days** of the occurrence of the event or notification of the PI of the event. This includes events that take place both at Washington University and at other secondary sites, if applicable.

10.6 Reporting to the FDA

The conduct of the study will comply with all FDA safety reporting requirements. **PLEASE NOTE THAT REPORTING REQUIREMENTS FOR THE FDA DIFFER FROM REPORTING REQUIREMENTS FOR HRPO/QASMC.** It is the responsibility of the Washington University principal investigator to report any unanticipated problem to the FDA as follows:

- Report any unexpected fatal or life-threatening adverse experiences (Section 10.1.4) associated with use of the drug by telephone or fax no later than **7 calendar days** after initial receipt of the information.
- Report any serious, unexpected adverse experiences (Section 10.1.2), as well as results from animal studies that suggest significant clinical risk within **15 calendar days** after initial receipt of this information.

All MedWatch forms will be sent by the investigator or investigator's team to the FDA at the following address or by fax:

Food and Drug Administration

Center for Drug Evaluation and Research
Division of Oncology Drug Products
[name]
[name]
FAX: [name]

Secondary sites must submit a completed MedWatch form to the Washington University PI and research coordinator within **4 calendar days** (for fatal or life-threatening adverse experiences) or **11 calendar days** (for serious, unexpected adverse experiences). The Washington University PI will be responsible for submitting all MedWatch forms from secondary sites to the FDA within the timeframes specified above.

10.7 Timeframe for Tracking Reportable Events:

Adverse events will be tracked for 30 days following the last day of study treatment, or until the start of a new chemotherapy/treatment, whichever comes first.

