5.0 INVESTIGATIONAL PLAN

5.1 Summary of Study Design

This is an open-label, single-arm, Phase II, biomarker study of patients with AML or MDS who are treated with 10 consecutive days of decitabine. FAB-M3 AML is excluded from this trial, because other well-tolerated options exist for the treatment of FAB-M3 acute promyelocytic leukemia. AML patients who are < 60 years old and have not received cytotoxic induction chemotherapy are also excluded, because cytotoxic therapy offers a curative possibility for these patients. MDS patients without cytopenias are also excluded because these patients can be followed with watchful-waiting.

All patients will undergo bone marrow biopsies pre-study, on Cycle 1 Day 10 \pm 1, and on Day 28 \pm 4 of Cycles 1, 2, 4, and 6. Following Cycle 6, bone marrow biopsies should be performed at the discretion of the treating physician to assess for relapse or progression. Patients will provide a skin biopsy sample pre-study. See Section 8.0 for details on correlative studies.

Patients will receive decitabine 20 mg/m²/day as a 1-hour infusion on consecutive Days 1-10 in 28-day cycles. The dose will be calculated based on actual patient weight at the beginning of each cycle.

Once AML patients achieve morphologic complete remission with incomplete blood count recovery (CRi) or MDS patients achieve a marrow complete response (Marrow CR) as defined in Section 9.0, decitabine administration may be decreased to 20 mg/m²/day for ten consecutive days every 6 weeks, to limit myelosuppressive toxicity and improve count recovery. After 2 cycles at 6 week intervals, the dose may be reduce to 20 mg/m²/day for five consecutive days in 6 week cycles, at the discretion of the treating physician. After two cycles of five consecutive days of treatment, if the patient meets the definition of CR with complete cytogenetic response as defined in Section 9.0, administration may further be decreased to three consecutive days per cycle at the discretion of the treating physician.

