6.0 DOSE MODIFICATIONS

A criterion for discontinuation of the study is a delay of > 8 weeks between any two cycles.

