6.1 Delay for Cytopenia or Infection

As cytopenias are a defining feature of AML and MDS, their presence alone does not generally warrant dose modifications or delays. Patients will receive four cycles of therapy without adjustment for any cytopenia. Following Cycle 4, dose modifications or delays for cytopenias will be made at the discretion of the investigator.

Patients with febrile neutropenia (temperature $\geq 38.5^\circ$ with ANC $< 1,000/\mu\text{l}$) or systemic infections should have treatment held until clinical resolution of the infection.

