6.2 Delay for Organ Dysfunction

If renal dysfunction (creatinine $\geq 3 \times$ institutional upper limit of normal) or hepatic dysfunction (bilirubin $\geq 2.5 \text{ mg/dl}$ or ALT/AST $\geq 3 \times$ institutional upper limit of normal) occurs, therapy may not resume until the abnormalities have resolved to below the limits stated above. If renal or hepatic dysfunction occurs during a treatment course, the next dose of decitabine should be held, and serum chemistries should be checked twice per week. Decitabine can be resumed at full dose when creatinine, bilirubin, ALT and AST are below the limits listed above.

For grade 3-4 non-hematologic toxicities related to decitabine, decitabine treatment should be delayed until recovery to baseline or to grade ≤ 1 . Decitabine may be reintroduced with a 50% dose reduction, or at full dose at the discretion of the investigator.

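### The stated adverse-event window closes 30 days after the last dose, inside an on-study hold that may last 8 weeks, so capture of late events depends on whether the patient is dosed again

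*Combined protocol and SAP*

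**What the plan says.** The end of adverse-event tracking is fixed in Section 10.7: "Adverse events will be tracked for 30 days following the last day of study treatment", or earlier if new treatment begins. Section 5.2.10 and footnote i of the flow chart in Appendix 2 also set 30 days for toxicity, counted from the last decitabine dose. After that, follow-up lists only later therapy, progression and death.

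The rules on holds are in Section 6:

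- 6.0: "A criterion for discontinuation of the study is a delay of > 8 weeks between any two cycles". The starting point of the 8 weeks is not given.
- 6.1: patients with febrile neutropenia or "systemic infections should have treatment held until clinical resolution of the infection".
- 6.2, renal or hepatic dysfunction: "therapy may not resume until the abnormalities have resolved to below the limits stated above". If it arises during a course, "the next dose of decitabine should be held, and serum chemistries should be checked twice per week".
- 6.2, related grade 3-4 non-hematologic toxicity: "decitabine treatment should be delayed until recovery to baseline or to grade" 1 or lower.

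Other passages suggest a different window. The flow chart marks adverse events as ongoing. Section 9.4.3 describes safety assessment over the whole study period. Section 14.2.4 counts patients who report an event at any time in the study and does not refer to 10.7. Section 15 asks for the adverse-event record when an event occurs, with no end date. No passage says whether tracking continues through a hold, or that an event still open when the window closes is followed to resolution.

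**The concern.** The last day of study treatment is known only in retrospect. A held patient who recovers and is dosed again gets a later last treatment day, so everything that happened during the hold is inside the window. A held patient who worsens and is never dosed again keeps the last dose before the hold as the last treatment day, and anything that begins or worsens more than 30 days later is outside it. Capture then depends on the outcome, and the loss falls on patients whose toxicity kept them from further treatment.

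At stake are the incidence, grade and attribution summaries in Section 14.2.4 and the toxicity summaries for the data and safety monitoring committee in Section 11. At least two further centers are planned (Section 14.3). Sites could reasonably apply different end dates, which would make the summaries inconsistent.

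**Working it through.** The plan states no figure of its own here. The check is calendar arithmetic.

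**Inputs**

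- Standard schedule (5.1): decitabine "as a 1-hour infusion on consecutive Days 1-10 in 28-day cycles". Last dosing day L = 10; next dose due on day D = 28 + 1 = 29.
- After response (5.1, 6.3): 10-day or 5-day courses every six weeks, so L = 10 or 5 and D = 42 + 1 = 43. A 3-day course (L = 3) is also allowed. Its interval is not restated, so six weeks is assumed.
- Tracking window (10.7): 30 days. Longest hold (6.0): 8 weeks = 56 days.
- The full course is assumed to have been given. If it is cut short, the window closes earlier.

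**Formulas**

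- Window closes on day L + 30.
- The hold limit depends on how 6.0 is read: (A) 56 days beyond the due date, D + 56; (B) 56 days from the last dose, L + 56; (C) 56 days from Day 1 to Day 1, 1 + 56 = 57.
- Days outside the window = hold limit minus closing day.

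| Schedule | Window closes | Next dose due | Limit A / B / C | Days outside A / B / C |
|---|---|---|---|---|
| 10 days in 28 | 10 + 30 = 40 | 29 | 85 / 66 / 57 | 45 / 26 / 17 |
| 10 days in 42 | 10 + 30 = 40 | 43 | 99 / 66 / 57 | 59 / 26 / 17 |
| 5 days in 42 | 5 + 30 = 35 | 43 | 99 / 61 / 57 | 64 / 26 / 22 |
| 3 days in 42 (assumed) | 3 + 30 = 33 | 43 | 99 / 59 / 57 | 66 / 26 / 24 |

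**Where the triggering event falls**

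On 28-day cycles, an event that blocks the next dose begins by Day 29. The window closes on Day 40, so the trigger begins at least 40 - 29 = 11 days before closure and is recorded. On six-week cycles the window closes before the next dose is due, by 43 - 40 = 3, 43 - 35 = 8 or 43 - 33 = 10 days. There a triggering event can itself begin outside the window.

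**Example**

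Two patients on the 28-day schedule are both held, and each has a new event on Day 50, which is within the hold limit on all three readings. If the first is dosed again after Day 50, the event precedes the new last treatment day and counts. If the second is never dosed again, the window closed on Day 40 and the event does not count under 10.7.

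**The case against.** The best defense is that the passages can be read together: adverse events are recorded throughout while the patient is on study, and the 30 days governs only what follows. Nothing tells staff to stop recording during a hold, and Section 11 requires continuing monitoring for serious toxicity. This is a sensible reading, but it is not what 10.7 says. Footnote i and Section 5.2.10 repeat the 30 days from the last dose, so the broader wording elsewhere conflicts with the rule and does not override it.

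A reader might infer something stronger: that the worst toxicities escape the safety data and that reported harm is biased downward by a material amount. The documents do not support that.

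- On the standard schedule the infection or organ toxicity that starts the hold is inside the window.
- Section 14.2.4 separately summarizes the maximum laboratory grade during the study, and blood counts and chemistries continue on schedule. Late laboratory toxicity therefore has another route into the results.
- Deaths are recorded in long-term follow-up and enter overall survival. What may be lost is a fatal event's grade and attribution as an adverse event.
- Under 6.1 the first four cycles are given without adjustment for cytopenia, so myelosuppression alone does not cause holds in that period.
- The largest gaps, 59 to 66 days, need reading A together with six-week cycles, which are open only to responders. Three-day courses also require complete remission with complete cytogenetic response.
- Section 5.3 lets the investigator stop treatment at any time, so a deteriorating patient need not stay on hold to the limit.

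All of these points stand. They limit the concern but leave the gap for late non-laboratory events, and on six-week cycles the first point does not apply.

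**Conclusion.** The point holds in a limited form. As written, the tracking rule is shorter than the permitted on-study hold and makes capture depend on later dosing. For a patient on 28-day cycles who is held for the full period and never dosed again, the last 17, 26 or 45 days are uncovered. The range arises because 6.0 does not say where its 8 weeks begins. What is exposed is new onset or worsening in that stretch, mainly of non-laboratory events, and the grade and attribution of a fatal event. On six-week cycles the exposure can include the trigger itself.

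These figures assume a literal reading of 10.7, a complete last course and a hold that runs to its limit. Any under-count would be downward, but its size cannot be computed: the documents give no rate of holds, of patients never dosed again, or of events after the window closes. In a single-arm trial with descriptive safety summaries this is a worthwhile, inexpensive correction and does not threaten the primary analysis.

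**What to change.** Reconcile Sections 6.0 to 6.2, 5.2.10, 10.7, 14.2.4 and Appendix 2 (including footnote i). Adverse-event capture should end at the later of (a) 30 days after the last dose and (b) the date the patient is taken off protocol treatment, unless new anti-leukemic therapy starts first. Use that single window in 10.7, 5.2.10, 14.2.4 and the flow chart. State in 6.0 where the 8 weeks is counted from; which starting point applies is for the sponsor to settle. No dose, hold or stopping rule changes.

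The cost is a short amendment, some extra adverse-event forms for patients whose last cycle ends in a hold, and slightly higher reported toxicity. Held patients already have scheduled blood counts and chemistries, so little new contact is needed. The change closes the gap during on-study holds. It does not equalize follow-up after treatment ends: a patient taken off treatment before Day 40 still has only the 30 days.
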